# 7.7 EXTENT OF EXPOSURE

Extent of exposure will be summarized for the treated set using descriptive statistics for days on treatment as well as frequency and percentage of subjects in the following categories: <42, 42 - <84, 84 - <126, 126 - <168, 168 - <179, 179 - <190,  $\ge 190$ .

#### 7.8 SAFETY ANALYSIS

All safety analyses will be performed on the treated set and other subject sets as appropriate.

#### 7.8.1 Adverse events

Unless otherwise specified, the analyses of AEs will be descriptive in nature. All analyses of AEs will be based on the number of subjects with AEs and not on the number of AEs. The reporting and analyses of AEs will follow the BI guideline (3). AEs will be coded with the most current version of MedDRA®.

For further details on summarization of AE data, please refer to (1, 3).

The analysis of AEs will be based on the concept of treatment emergent AEs. That means that all AEs occurring between the date of the first administration of trial treatment till the date of the last administration of trial treatment + residual effect period will be assigned to the ontreatment period. All AEs occurring before the first administration of trial treatment will be assigned to 'screening' and all AEs occurring after the residual effect period will be assigned to 'follow-up'. For details on the treatment definition, see Section 6.1.

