4.1.4 Drug assignment and administration of doses for each patient

Dispensing of medication kits for the double-blind treatment period will begin at Visit 2. Throughout the treatment period, 2 trial medication kits will be provided at each visit. Medication assignment will be provided through IRT. The assigned medication kit numbers must be entered in the eCRF, and the corresponding medication kits must be given to the patient. The duration of treatment is 26 weeks. At each of the visits, patients will receive supplies for a total of 4 weeks.

The first dose of study medication will be taken at the end of Visit 2 under supervision of the investigator or delegated site staff, after all Visit 2 assessments have been completed. In case the Visit 2 is split into 2 sequential days, the first dose of study medication should be taken on the second day of the split visit, after all Visit 2 assessments have been completed.

Throughout the study, patients should be instructed to take 1 tablet orally with water and with or without food after waking up. If a dose is missed by more than 12 hours, that dose should be skipped and the next dose should be taken as scheduled.

Patients should be instructed **not** to take their study medication at home on the day of the clinic visit as patients will be dosed at the site. Dosing should occur approximately 24 hours after the drug administration from the preceding day.

Page 44 of 112

Proprietary confidential information © 2023 Boehringer Ingelheim International GmbH or one or more of its affiliated companies

The last dose of study medication should be taken on the day before the EoT Visit. In case the EoT Visit is split into 2 sequential days, the last dose of study medication should be taken on the day before the first day of the split visit.

On longer visit days the dosing may occur in the afternoon.

A dose reduction of Iclepertin is not possible.

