5.2.6.2 Adverse event collection and reporting

5.2.6.2.1 **AE** Collection

The investigator shall maintain and keep detailed records of all AEs in the patient files.

The following must be collected and documented on the appropriate eCRF(s) by the investigator:

For patients *who* roll-over to the extension trial:

o From signing informed consent (1346-0012) onwards until first dose of trial medication in the extension trial: all AEs (serious and non-serious) and all AESIs. Updates to concomitant therapy should also be included until first dose of trial medication in the extension trial.

Note: Updates for SAEs and/or AESIs that are ongoing at the time of rollover to the extension trial must also be updated in the parent trial (1346-0012) in addition to being recorded in the extension trial, as long as the database for the parent trial is not locked. On the SAE form, updates for events reportable on the SAE form with onset in the parent trial are only reported into the parent trial.

For patients who do not roll-over to the extension trial:

- From signing the informed consent onwards until the 28 days (Follow-up 6 visit) after the EOT visit: all AEs (serious and non-serious) and all AESIs.
- After the individual patient's end of study: The investigator does not need to actively monitor the patient for new AEs but should only report any occurrence of cancer and trial treatment related SAEs and trial treatment related AESIs of which the investigator may become aware of by any means of communication, e.g. phone call. Those AEs should be reported on the BI SAE form (see section 5.2.6.2.2), but not on the eCRF.

For patients who permanently discontinue trial medication prematurely

- From signing the informed consent onwards until the 28 days after the early EOT visit: all AEs (serious and non-serious) and all AESIs.
- From Follow-up visit 6 up to the individual patient's planned end of study: until the individual patient's planned end of the study, the investigator must report treatment related SAEs / AESIs and the following events regardless of causal relationship:
 - anaemia,
 - all SAEs from C-SSRS assessments,
 - any occurrences of cancer
 - all deaths/ fatal AEs.

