#### 6. GENERAL ANALYSIS DEFINITIONS

## 6.1 TREATMENT(S)

For basic study information on treatments to be administered, assignment of treatment groups, select of doses, see CTP Section 4.

Table 6.1: 1 lists the two treatment groups in this study. Table 6.1: 2 defines the analysing treatment period for safety analyses. For this study, the residual effect period (REP) is defined as 12 days after the last dose of trial medication.

Table 6.1: 1 Treatment descriptions

Long Name	Short Name	
Placebo	Placebo	
Iclepertin 10 mg QD	Iclepertin 10 mg	

Table 6.1: 2 Analysing treatment periods (same for all treatment groups)

Analysing Treatment Period	Start Date	End Date
Screening period	Date of informed consent	Date of the first treatment administration – 1 day
On-treatment period	Date of the first treatment administration	Date of the last treatment administration + REP
Post-treatment period	Date of the last treatment administration + REP + 1 day	Date of the last per protocol visit
Strictly on-treatment period	Date of the first treatment administration	Date of the last treatment administration
4-week withdrawal period	Date of last treatment administration + 1 day	Date of last treatment administration + 28 day

REP is the residual effect period which is defined as 12 days after the last dose of trial treatment.

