### Sleep disorder

Sleep disorder related AE search terms are based upon the FDA Medical Queries (FMQs) of Insomnia (broad) and Somnolence (broad). Refer to Table 7.8.1: 4 for a list of MedDRA preferred terms in each of the groupings.

Table 7.8.1: 4 MedDRA preferred terms for user-defined AE categories of sleep disorder AEs

User-defined AE category	MedDRA preferred terms		
FMQ Insomnia (broad)	Advanced sleep phase	Primary insomnia	
	Behavioural induced insufficient sleep syndrome	Psychophysiologic insomnia	
	Circadian rhythm sleep disorder	Shift work disorder	
	Delayed sleep phase	Sleep disorder due to general medical condition, insomnia type	
	Dyssomnia	Sleep disorder due to general medical condition, mixed type	
	Early morning awakening	Terminal insomnia	
	Fatal familial insomnia	Dysfunctions associated with sleep stages or arousal from sleep	
	Hyposomnia	Dyssomnia NOS	

	Initial insomnia	Jet lag
	Insomnia	Microsleep
	Insomnia exacerbated	Sleep deficit
	Insomnia NEC	Sleep disorder
	Insomnia related to another mental condition	Sleep disorder due to a general medical condition
	Irregular sleep phase	Sleep disorder NOS
	Irregular sleep wake rhythm disorder	Sleep disorder therapy
	Middle insomnia	Sleep inertia
Non-24-hour sleep-wake disorder		Sleep study abnormal
	Poor quality sleep	
FMQ Somnolence (broad)	Central nervous system depression NOS	Sedation aggravated
	Consciousness fluctuating	Somnolence
	Depressed level of consciousness	Somnolence neonatal
	Hypersomnia	Stupor
	Infant sedation	Altered state of consciousness
	Lethargy	Fatigue
	Neonatal oversedation	Fatigue aggravated
	Primary hypersomnia	Prostration
	Sedation	Sluggishness

An overall summary of adverse events will be presented, including frequency of schizophrenia relapse. The frequency of subjects with AEs will be summarised by treatment, primary system organ class (SOC) and preferred term (PT). The SOCs will be sorted by default in descending frequency and PTs will be sorted in descending frequency within an SOC in the iclepertin arm. Separate tables will be provided for patients with

- Related AEs
- Serious AEs
- Serious related AEs
- AESIs
- Other significant AEs
- AEs leading to death
- AE leading to discontinuation of trial medication
- AEs occurred with incidence in the preferred term >2%
- AEs suggestive of abuse potential or related to CNS depressant effects
- AEs in user-defined AE categories
- AEs occurred during the follow-up period.

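### The descriptive follow-up AE table has no fixed end, so it mixes short, fully collected windows (completers) with long, partly selective ones (early stoppers who stay in the trial)

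*SAP*

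**What the plan says.** **Period.** In SAP 6.1, "the residual effect period (REP) is defined as 12 days after the last dose of trial medication". Table 6.1: 2 starts the post-treatment period at "Date of the last treatment administration + REP + 1 day" and ends it at "Date of the last per protocol visit". SAP 7.8.1 says that "all AEs occurring after the residual effect period will be assigned" to follow-up and refers back to 6.1 for details. I read follow-up there as the post-treatment period, because no other row of the table begins after the residual effect period.

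**Table.** The list of separate AE tables at the end of SAP 7.8.1 includes "AEs occurred during the follow-up period". The measure is fixed earlier in the section: "All analyses of AEs will be based on the number of subjects with AEs and not on the number of AEs". The visible text gives this table no cap, no time-at-risk adjustment and no split by completion status.

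**Who is followed, and for what.** Protocol 6.2.5 ends a completer's study at Follow-up 6. It keeps early stoppers who continue in the trial to planned Visit 11, or EOT + 28 days if that is later. Under Protocol 5.2.6.2.1 all AEs are collected up to 28 days after EOT or early EOT. For early stoppers after Follow-up 6 the rule narrows: "the investigator must report treatment related SAEs / AESIs and the following events regardless of causal relationship". The listed events are anaemia, SAEs from the C-SSRS, cancers and deaths. The flow chart marks AEs at every visit, but the footnote to Protocol Table 6.2.3.4: 1 sends early discontinuers to this narrower rule.

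**Elsewhere.** Protocol 7.2.5 and SAP Table 6.1: 2 also define a 4-week withdrawal period of fixed length, from last dose + 1 to last dose + 28 days.

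**The concern.** A percentage of subjects with an event is interpretable when patients are observed for similar times under one collection rule. Here neither condition holds within the table.

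- **Across event types.** In an early stopper who stays, anaemia or a C-SSRS SAE can enter the count months after the last dose. A non-serious headache or somnolence cannot enter once Follow-up 6 has passed. Percentages by preferred term therefore rest on different observation times.
- **Across arms.** The rule is the same in both arms. If the arms differ in how many patients stop, when they stop, or how many stay afterwards, their observation times differ, and the percentages move with that as well as with risk.

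Stopping is expected to be common: Protocol 7.5 projects 30–40%, which is 0.30 × 293 ≈ 88 to 0.40 × 293 ≈ 117 patients per arm. A difference between arms is possible. In the phase II figures of Protocol Table 1.4.2:1, haemoglobin fell by 3.3 g/L on 10 mg and 0.5 g/L on placebo. Low haemoglobin is a withdrawal criterion, and anaemia is one of the events still collected afterwards.

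**Working it through.** The documents state no length for this period, so there is no plan figure to reproduce. The lengths follow from its definitions.

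**1. Completers.** The protocol (4.1.4) says "The last dose of study medication should be taken on the day before the EoT Visit", so last dose = EOT − 1. Follow-up 6 is at EOT + 28, with a +7 day window, i.e. last dose + 29 to + 36.

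- Days in the table: 29 − 12 = 17, up to 36 − 12 = 24. All are under full collection.

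**2. Early stoppers who stay to Visit 11.** Let d be the last-dose day, e the delay to early EOT (0–7 days, Protocol 6.2.3.4) and w the Follow-up 6 window (0–7 days). Visit 11 is planned for Day 183.

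- Total days = max(183, d + e + 28 + w) − (d + 12)
- Full-collection days = 16 + e + w, i.e. 16–30
- Selective days = the remainder

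| Last-dose day | Total days | Selective days | Selective share |
|---|---|---|---|
| 1 | 170 | 140–154 | 82–91% |
| 43 | 128 | 98–112 | 77–88% |
| 85 | 86 | 56–70 | 65–81% |
| 106 (Week 15) | 65 | 35–49 | 54–75% |
| 127 | 44 | 14–28 | 32–64% |
| 148 | 23–30 | 0–7 | 0–30% |

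So 170 days is the extreme case of a single dose on Day 1. The window is mostly selective up to about Week 15 and not reliably so after that. The ±3 days on Visit 11 shift the maximum to 167–173.

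**3. Share of person-time.** This needs assumptions the documents do not supply:

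- stopping days are spread evenly over Days 1–175, which gives a mean window of about 85 days for stoppers who stay;
- stoppers who leave complete safety follow-up and contribute about 20 days (possible range 16–30);
- the share of stoppers who stay, r, is 25%, 50% or 100%. Protocol 7.5 expects 25–50% of early dropouts to have efficacy data after stopping; I use that as a proxy, with 100% as the ceiling.

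Mean days per stopper, m = 85r + 20(1 − r): 36.25, 52.5 and 85. With stopping proportion p and completer window c, the stoppers' share is pm / [pm + (1 − p)c].

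| r | c | Share, p = 30% | Share, p = 40% | Days per patient, 40% vs 30% stopping |
|---|---|---|---|---|
| 25% | 17 | 48% | 59% | 24.7 vs 22.8 (+8%) |
| 25% | 24 | 39% | 50% | 28.9 vs 27.7 (+4%) |
| 50% | 17 | 57% | 67% | 31.2 vs 27.7 (+13%) |
| 50% | 24 | 48% | 59% | 35.4 vs 32.6 (+9%) |
| 100% | 17 | 68% | 77% | 44.2 vs 37.4 (+18%) |
| 100% | 24 | 60% | 70% | 48.4 vs 42.3 (+14%) |

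For example, at r = 25%, c = 24, p = 30%: 0.30 × 36.25 = 10.9; 0.70 × 24 = 16.8; 10.9 / 27.7 = 39%.

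**4. Sensitivity to the leavers.** If leavers contributed nothing, then at r = 25%, m = 21.25. With c = 24 and p = 30% the share falls to 6.4 / (6.4 + 16.8) = 28%. Across r = 25–50% and c = 17–24 the arm contrast runs from about −1% to 10%.

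**The case against.** The case for leaving the plan alone has real weight.

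- **The main safety results do not use this table.** Treatment-emergent AEs stop at last dose + 12 days. Early post-treatment risk can be read from the withdrawal analysis, which has a fixed window inside full collection. Safety analyses are descriptive, with no hypothesis tests. This stands, and it makes the point minor.
- **The rule is the same in both blinded arms.** A reader might infer that the arm percentages reflect stopping behaviour rather than post-treatment risk. The documents do not support that. The arm comparison is distorted only if the number, timing or retention of stoppers differs by arm. The non-comparability between event types, by contrast, needs no arm difference.
- **Large person-time figures depend on retention.** A share of 68–77% and an 18% arm contrast require every stopper to stay to Visit 11 and completers to contribute only 17 days. Protocol 6.2.5 provides for stoppers who leave, and Protocol 3.3.4.3 for consent withdrawal with no further data. Safety retention may still exceed efficacy retention, since the last follow-up option in Protocol Table 6.2.3.4: 1 keeps safety data only. The full range has to be shown.
- **Internal guides.** SAP 7.8.1 defers some AE reporting detail to sponsor guides that are not available here. They may add a footnote or a split, but the SAP text does not say so.

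The fixed withdrawal window is a separate analysis. It neither caps nor replaces the follow-up table.

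**Conclusion.** The point holds as a minor one, confined to a single descriptive table. As defined, the table combines 17–24 days of full collection in completers with up to 170 days in early stoppers who stay. For those who stop before about Week 15, most of these days are under the selective rule. Percentages by preferred term are not comparable across event types: anaemia, C-SSRS SAEs, cancers and deaths are collected for longer. The arm comparison is vulnerable to differential stopping or retention.

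At 30–40% stopping, early stoppers supply about 39–77% of follow-up person-time, and a 40% versus 30% stopping difference changes follow-up time per patient by about 4–18%. Both ranges rest on evenly spread stopping, 25–100% retention, a 17–24 day completer window and about 20 days from leavers. If leavers contribute less, both lower ends fall. It would be wrong to conclude that the trial's AE evaluation as a whole is biased: the treatment-emergent tables and the 4-week withdrawal analysis are untouched.

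**What to change.** In SAP 7.8.1, end the tabulated follow-up AE period at last dose + 28 days, the end date that Table 6.1: 2 already uses for the withdrawal period. The table then covers days 13 to 28 after last dose: 28 − 12 = 16 days for completers and for early stoppers still in follow-up. All of it lies within full collection, because early EOT + 28 is never before last dose + 28, and a completer's Follow-up 6 is at last dose + 29 or later.

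Show later AEs in a separate table or listing. For early stoppers, restrict it to the event types collected after Follow-up 6 and use those still being followed as the denominator.

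Ending the table at Follow-up 6 would be less effective: windows would still be 16–30 days for early stoppers against 17–24 for completers.

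The cost is one end-date rule and one extra table, with no new data collection.

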## Adverse events of special interest (AESIs)

A hepatic injury is defined by the following alterations of hepatic laboratory parameters:

- an elevation of AST and / or ALT  $\geq$  3 fold ULN combined with an elevation of total bilirubin  $\geq$  2 fold ULN measured in the same blood draw sample; and / or
- marked peak aminotransferase (ALT and / or AST) elevations  $\geq 10$  fold ULN.

See CTP Section 5.2.6.1.

#### Other significant AEs

According to ICH E3, in addition to deaths and serious adverse events, 'other significant' AEs need to be listed in the clinical trial report. These will include:

- 1. Any adverse events that led to an intervention, such as withdrawal of drug treatment.
- 2. Marked haematological and other lab abnormalities or lead to significant concomitant therapy as identified by the Clinical Monitor/Investigator during medical quality review at TOM.

# AEs suggestive of abuse potential or related to CNS depressant effects

In support of an evaluation of human abuse potential, user-defined AE categories (UDAEC) are defined in Table 7.8.1: 1 for AEs suggestive of abuse potential and AEs related to CNS depressant effects.

Table 7.8.1: 1 MedDRA preferred terms for user-defined AE categories of AEs suggestive of abuse potential or related to CNS depressant effects

User-defined AE category	MedDRA preferred terms	
Drug abuse, dependence,	Accidental death	Intentional overdose
withdrawal and substance- related disorders, including	Drug abuse	Muscle rigidity
diversion	Accidental overdose	Nasal necrosis
	Accidental poisoning	Nasal septum perforation
	Dependence	Nasal septum ulceration
	Drug abuser	Needle track marks
	Product administered at inappropriate site	Neonatal complications of substance abuse
	Drug dependence	Overdose
	Drug detoxification	Poisoning
	Drug dependence antepartum	Poisoning deliberate
	Drug dependence, postpartum	Substance dependence
	Drug diversion	Prescription form tampering
	Drug tolerance	Product tampering
	Drug tolerance increased	Product used for unknown indication
	Toxicity to various agents	Rebound effect
	Drug use disorder	Seizure
	Drug use disorder antepartum	Status epilepticus
	Drug use disorder, postpartum	Substance abuse
	Drug withdrawal convulsions	Substance abuser
	Drug withdrawal headache	Substance use
	Drug withdrawal syndrome	Substance use disorder
	Drug withdrawal syndrome neonatal	Substance-induced mood disorder
	Generalised tonic-clonic seizure	Substance-induced psychotic disorder

	Hangover	Treatment noncompliance
	Intentional product misuse	Withdrawal syndrome
Euphoria-related adverse	Dizziness	Feeling drunk
events	Euphoric mood	Feeling of relaxation
	Feeling abnormal	Inappropriate affect
CNS depressant effects	Depressed level of consciousness	Sedation
	Fatigue	Sluggishness
	Hypersomnia	Somnolence
	Lethargy	Stupor
	Loss of consciousness	
Stimulation and anxiety-	Agitation	Morbid thoughts
related adverse events	Anxiety	Nervousness
	Anxiety disorder	Panic attack
	Anticipatory anxiety	Panic disorder
	Energy increased	Panic reaction
	Fear	Psychogenic tremor
	Fear of death	Psychomotor hyperactivity
	Feeling jittery	Restlessness
	Generalised anxiety disorder	Tension
	Hypervigilance	
Perceptual disturbances /	Abnormal dreams	Hypoaesthesia
psychotomimetic effects	Acute psychosis	Ideas of reference
	Aggression	Illogical thinking
	Alice in wonderland syndrome	Illusion
	Altered state of consciousness	Incoherent
	Altered visual depth perception	Indifference
	Anger	Jamais vu
	Communication disorder	Loose associations
	Confusional state	Magical thinking
	Consciousness fluctuating	Nightmare
	Déjà vu	Paranoia
	Delirium	Paroxysmal perceptual alteration
	Delusion	Psychotic behaviour
	Delusion of grandeur	Psychotic disorder
	Delusion of reference	Psychotic symptom
	Delusion of replacement	Reactive psychosis
	Delusional perception	Rebound psychosis
	Derailment	Sensory disturbance
	Disinhibition	Sensory level abnormal
	Disorientation	Slow speech
	Dysarthria	Somatic delusion
	Flight of ideas	Somatic hallucination

	Formication	Staring
	Hallucination	Suspiciousness
	Hallucination, auditory	Tangentiality
	Hallucination, gustatory	Thinking abnormal
	Hallucination, olfactory	Thought blocking
	Hallucination, synaesthetic	Thought broadcasting
	Hallucination, tactile	Thought insertion
	Hallucination, visual	Thought withdrawal
	Hallucinations, mixed	Transient psychosis
	Hostility	
Dissociation	Daydreaming	Hypogeusia
	Depersonalisation/derealisation disorder	Metamorphopsia
	Derealisation	Ocular discomfort
	Diplopia	Oral dysaesthesia
	Dissociation	Oral hyperaesthesia
	Dissociative disorder	Pain threshold decreased
	Dissociative identity disorder	Paraesthesia
	Dysaesthesia	Paraesthesia oral
	Dysaesthesia pharynx	Pharyngeal hypoaesthesia
	Dysgeusia	Pharyngeal paraesthesia
	Dysmetropsia	Photophobia
	Feeling cold	Photopsia
	Feeling hot	Synaesthesia
	Feeling of body temperature change	Time perception altered
	Flashback	Tinnitus
	Hyperacusis	Vision blurred
	Hyperaesthesia	Visual impairment
	Hypersensitivity	
Mood disorders and	Abnormal behaviour	Depressive delusion
disturbances	Affect lability	Depressive symptom
	Affective disorder	Disturbance in social behaviour
	Anhedonia	Emotional disorder
	Antisocial behaviour	Emotional distress
	Apathy	Feeling of despair
	Asocial behaviour	Flat affect
	Attention-seeking behaviour	Hypomania
	Belligerence	Impatience
	Blunted affect	Impulse-control disorder
	Compulsive cheek biting	Impulsive behaviour
	Compulsive handwashing	Irritability
	Compulsive hoarding	Mania

	Compulsive lip biting	Mood altered	
	Compulsive sexual behaviour	Mood swings	
	Compulsive shopping	Parasomnia	
	Obsessive-compulsive symptom	Personality change	
	Compulsions	Sleep talking	
	Confusional arousal	Sleep terror	
	Depressed mood	Sleep-related eating disorder	
	Depression	Somnambulism	
Mental and cognitive	Amnesia	Impaired driving ability	
impairment	Amnestic disorder	Impaired reasoning	
	Anterograde amnesia	Judgement impaired	
	Balance disorder	Memory impairment	
	Bradyphrenia	Mental disability	
	Change in sustained attention	Mental disorder	
	Cognitive disorder	Mental impairment	
	Confabulation	Mental status changes	
	Coordination abnormal	Paramnesia	
	Distractibility	Psychomotor retardation	
	Disturbance in attention	Psychomotor skills impaired	
	Dyslogia	Retrograde amnesia	
	Executive dysfunction	Transient global amnesia	

